7.2.1. Computation of the Primary Endpoint

A participant will be considered operationally tolerant if they have successfully withdrawn from all immunosuppression and remain off all immunosuppression for 52 weeks, have no evidence of rejection since enrollment, and have a liver biopsy at 52 weeks read centrally that shows both

the absence of rejection and has histological stability consistent with Table 1. Otherwise, the participant will be considered non-tolerant.

Participants who are non-evaluable at 52 weeks following discontinuation of all immunosuppression time point due to inadequate follow-up, lack of biopsy, or premature study termination will be considered non-tolerant for the purpose of evaluating the primary endpoint.

Biopsy results may be as early as 44 weeks following the discontinuation of all immunosuppression. This is because a for-cause liver biopsy visit that occurs within 8 weeks prior to a scheduled protocol visit takes the place of a scheduled protocol visit, thus a for-cause biopsy within 8 weeks of Visit 204 can be evaluated for the primary endpoint. Any biopsies done earlier than 44 weeks prior to discontinuation of all immunosuppression will be reviewed for inclusion by the SMT on a case by case basis. Any primary endpoint biopsy performed later than 52 weeks (+4 weeks) will be utilized.

All immunosuppression dosing information is collected as a daily record. Therefore, any immunosuppression information will not have an associated window.

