APPENDIX 2. SCHEDULE OF EVENTS – POST WITHDRAWAL FOLLOW-UP

IMPORTANT NOTE: For the duration of the COVID-19 pandemic, follow the COVID-19 Modified Appendix 2-C instead (per Section 6.2).

IS Withdrawal Follow-up Weeks ¹	0	13	26	52	78	104	130	156
Visit Number ^{2,3}	201 ⁴	202	203	204	205	206	207	208
General Assessments								
Limited physical exam	X	X	X	X	X	X	X	X
Vital signs including weight	X	X	X	X	X	X	X	X
Quality of Life Questionnaires	X		X	X	X	X	X	X
Status Change since prior visit ⁵	X	X	X	X	X	X	X	X
Telephone consultation ⁶	X							X
ECG					Prior to restarting tacrolimus ⁷			
Local Clinical Laboratory Assessments								
LFTs ⁸		Every 4 weeks		Every 8 weeks			Every 12 weeks	
CBC w/differential	X	X	X	X	X	X	X	X
Comprehensive metabolic panel, includes LFTs	X	X	X	X	X	X	X	X
Liver biopsy				X				X
Mechanistic Laboratory Assessments								
Frozen PBMC collection	X		X	X		X		X
Serum collection	X		X	X		X		X
Whole blood collection	X		X	X		X		X
Urine pellet collection	X		X	X		X		X
Fecal collection ⁹	X		X	X		X		X
Liver biopsy collection				X				X

¹ The assessments outlined in Appendix 2 should be completed for all participants who initiated and successfully completed immunosuppression withdrawal. Follow-up should begin within 2 weeks of the date of completion of the participant's last taper level (see section 3.1.3).

² If a for-cause liver biopsy is needed, follow all assessments specified in Appendix 5. If the for-cause biopsy occurs within 8 weeks prior to a scheduled protocol visit, complete all clinical and mechanistic assessments listed in Appendix 5 at the time of the for-cause biopsy. The for-cause biopsy visit will take the place of the scheduled protocol visit.

³ If a participant restarts immunosuppression after successfully completing immunosuppression withdrawal, follow the assessments listed in Appendix 4. **Appendix 2 visits to be completed in addition and concurrently with Appendix 4.**

⁴ For any participant requesting early termination from the study, follow all assessments specified here, Visit 201.

⁵ Includes assessment of change in adverse events and concomitant medications. Changes should be recorded in eCRFs as appropriate.

⁶ Complete following the performance of each liver function test assessment done outside of a transplant center clinical visit; AEs and concomitant medications to be reviewed.

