4. ANALYSIS SAMPLES

Intent to treat (ITT) sample: All participants who provide informed consent for study participation and begin immunosuppression withdrawal.

[figure not shown]
Per protocol (PP) sample: All participants who attempt immunosuppression withdrawal and do not have any unacceptable major protocol deviations. Subjects experiencing major protocol deviations may be excluded at the discretion of the study team during a blinded review of deviations.

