7.1.2. Assessment Time Windows

Unscheduled visits may also occur throughout the study.

All data will be included in analyses, regardless of time of assessment, unless explicitly stated.

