7.2.2. Primary Analysis of the Primary Endpoint

The proportion of participants who are identified as operationally tolerant with a corresponding two-sided 95% exact binomial confidence interval. This will be analyzed using the ITT and PP samples.

The results will be presented in a table as shown below.

	Total (N = XX)
	n (%)
Proportion Tolerant [1]	X (X.X%)
95% Exact Binomial Confidence Interval	(X.X, X.X)

[1] Subjects who remain off immunosuppression for at least 52 weeks without evidence of rejection and demonstrate histological stability, as determined by a biopsy performed 52 weeks after the completion of immunosuppression withdrawal, are considered tolerant.

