8.5.3. Other Safety Measures

8.5.3.1. IS Minimization

The baseline IS dose (dose immediately prior to the initiation of withdrawal) will be compared to IS dose at the end of study participation for each subject that initiated IS withdrawal. Each comparison will be classified as 'more', 'less', or the 'same'. The count and percentage of each category will be presented.

For subjects that do not switch medication types (i.e. start on tacrolimus monotherapy and finish on tacrolimus monotherapy) this will be a straight numeric comparison of total daily dose.

For subjects on multiple drugs or subjects that switch medication types (i.e. start on tacrolimus and switch to cyclosporine), the SMT will complete a blinded review of the data and make a determination of 'more', 'less' or 'same'.

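### SAP 7.2.1: the rule for early primary-endpoint biopsies is misprinted and, read as intended, lets the SMT accept a biopsy before week 44 with no criteria or stated blinding

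*SAP*

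**What the plan says.** SAP 7.2.1 defines tolerance by 52 weeks off all immunosuppression, no rejection since enrolment, and a week-52 biopsy that is clean on the central read. Anyone else is non-tolerant. On timing it says three things.

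- **Earliest biopsy by rule.** "Biopsy results may be as early as 44 weeks following the discontinuation of all immunosuppression". The reason given is that a for-cause biopsy shortly before Visit 204 replaces that visit. Protocol 6.1.1 and Appendix 2, note 2, are the source ("If the for-cause biopsy occurs within 8 weeks prior to a scheduled protocol visit", the for-cause visit stands in for the scheduled one).
- **Earlier biopsies.** "Any biopsies done earlier than 44 weeks prior to discontinuation of all immunosuppression will be reviewed for inclusion by the SMT", case by case. No criteria follow, and nothing is said about what the SMT may see.
- **Late biopsies.** An endpoint biopsy after week 52 + 4 is used, with no upper limit and no review.

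The default for missing histology is clear. SAP 7.2.1 says that participants who cannot be evaluated at week 52 "due to inadequate follow-up, lack of biopsy, or premature study termination will be considered non-tolerant". Protocol 9.2.1 also counts a participant without a week-52 biopsy as a failure and mentions no SMT review. The table footnote in SAP 7.2.2 describes tolerance "as determined by a biopsy performed 52 weeks after the completion of immunosuppression withdrawal, are considered tolerant".

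Elsewhere the SAP does state blinding for discretionary decisions. Under section 4, participants with major deviations "may be excluded at the discretion of the study team during a blinded review of deviations". Under 8.5.3.1, for dose comparisons across drugs, "the SMT will complete a blinded review of the data and make a determination of" more, less or same.

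**The concern.** The sentence sits in the computation of the primary endpoint, and its wording does not do its job. A programmer who follows it literally finds no provision for a biopsy at, say, week 40 after discontinuation. One who follows the evident intention finds a committee decision with no stated basis.

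The second reading is the one that matters. The trial is open label, and the SAP specifies blinded review for two other discretionary decisions but not for this one. Where no later biopsy exists, the default label is non-tolerant, so accepting an early biopsy can only turn a failure into a success. The same label also defines the groups for the fibrosis, eGFR and quality-of-life comparisons, the denominator for 3-year freedom from rejection, and the outcome in the logistic regression (SAP Table 7-2).

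**Working it through.** **1. The plan's own precision.** Inputs from Protocol 9.3: n = 60, expected proportion 40% or 60%. The exact (Clopper-Pearson) limits for x successes are the 0.025 quantile of Beta(x, n − x + 1) and the 0.975 quantile of Beta(x + 1, n − x).

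- 24/60 = 40.0%: 27.6% to 53.5%
- 36/60 = 60.0%: 46.5% to 72.4%

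Both agree with the protocol.

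**2. What the 44-week limit means.** Visit 204 is at week 52 after discontinuation. A for-cause biopsy up to 8 weeks before it may replace it: 52 − 8 = 44 weeks *following* discontinuation. The protocol window for the visit itself is 52 ± 4, or weeks 48 to 56. No calculation in the paragraph gives 44 weeks *before* discontinuation.

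**3. What the printed sentence covers.** Protocol 3.2 gives about 8 weeks of screening and about 24 to 45 weeks of withdrawal. A biopsy at the start of screening therefore lies about 24 + 8 = 32 to 45 + 8 = 53 weeks before discontinuation. To lie more than 44 weeks before it, withdrawal must last more than 44 − 8 = 36 weeks. A biopsy taken during withdrawal qualifies only in about the first week of a 45-week taper (45 − 44 = 1). These are typical figures, not bounds: a rescreened participant may reuse an older eligible biopsy (Protocol 6.4.1; Appendix 1A, note 17). That is still an eligibility biopsy. No biopsy after discontinuation is covered.

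**4. Who is affected under the intended reading.** All of these must hold:

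- a biopsy after discontinuation but before week 44;
- no endpoint biopsy at week 44 or later, although a for-cause biopsy before week 44 does not replace Visit 204 and a biopsy after week 56 is accepted without review;
- 52 weeks off all immunosuppression;
- no rejection since enrolment;
- a clean central read on the early biopsy.

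For such a participant the default is non-tolerant, and the SMT's decision alone changes it.

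**5. Size.** Each one adds 1/60 = 1.7 points. The documents do not give the number; 0 to 3 is an assumption. The starting points are 40% (Protocol 9.3) and 30%, the lower end of the 30–40% expected in Protocol 1.3.2.

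| Accepted | From 24/60 (exact 95% CI) | From 18/60 (exact 95% CI) |
|---|---|---|
| 0 | 40.0% (27.6–53.5) | 30.0% (18.8–43.2) |
| 1 | 41.7% (29.1–55.1) | 31.7% (20.3–45.0) |
| 2 | 43.3% (30.6–56.8) | 33.3% (21.7–46.7) |
| 3 | 45.0% (32.1–58.4) | 35.0% (23.1–48.4) |

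The largest shift shown is 3 × 1.7 = 5 points, well inside the planned ±13.

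**The case against.** The intended meaning is obvious from the sentence before, so the misprint on its own need mislead no one. The two faults are also alternatives: read literally, the SMT has no say over any biopsy after discontinuation; read as intended, the wording slip has no further effect. That stands, and the point therefore rests on the intended reading.

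The affected group is very small. Visit 204 remains due after an early for-cause biopsy, and a missed one can be made up late. The SMT decides only inclusion; the histology comes from the central read. Investigators and participants are blinded to individual biomarker results until the end of the study (Protocol 3.1). All of this stands, although that blinding names neither the SMT nor the biopsy read.

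A reader might infer that the SAP contradicts itself on timing, because 7.1.2 says "All data will be included in analyses, regardless of time of assessment, unless explicitly stated". It does not: that rule gives way to explicit statements, and 7.2.1 is one. The non-tolerant default is settled, and what is left is one open exception to it.

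A reader might also infer that the SMT will judge with the results in view, or that the tolerance rate will be materially inflated. The documents support neither. They do not say what the SMT sees, and nothing in them shows that even one participant would qualify.

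Finally, it could be argued that a participant who is well and off treatment at week 52 is tolerant in substance. Protocol 3.4 weakens that argument: it notes reports of subclinical rejection with normal liver tests, so being well at week 52 does not replace the later histology.

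**Conclusion.** A minor point that holds. It is certain that *prior to* is wrong and that the text gives neither criteria nor blinding for this decision. Read as intended, the sentence creates an exception to the failure rule in Protocol 9.2.1 that the protocol does not provide. For a participant with no later biopsy, it can move the label only from non-tolerant to tolerant.

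The size is 1.7 points per participant with n = 60, for a number that the documents do not give and that may be zero. The endpoint is descriptive, so no formal decision changes. No direction is claimed for participants who also have a biopsy at week 44 or later.

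**What to change.** In SAP 7.2.1:

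1. Change *prior to* discontinuation to *following* discontinuation.
2. In the primary analysis, score participants whose only biopsy after discontinuation is before week 44 as non-tolerant. This matches Protocol 9.2.1 and the default that 7.2.1 already applies when there is no biopsy.
3. If the SMT review is kept, use it only for a supportive row that counts accepted early biopsies. Decide each case before database lock and blind to the biopsy reads.

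The cost is a corrected phrase, one or two sentences of SAP text and at most one extra table row. The primary estimate may be slightly lower. Nothing changes in when biopsies are taken or how participants are managed.

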6.7.3 Presumed Rejection

Every effort should be made to confirm all episodes of suspected rejection with a biopsy. However in cases where this is medically contraindicated, participants may be treated empirically based on clinical suspicion. Participants with allograft dysfunction who are treated with an increase in immunosuppression without a confirmatory biopsy will be considered to have **presumed rejection**.

Participants with presumed rejection must undergo a biopsy within a week after initiation of treatment for allograft dysfunction, unless medically contraindicated. If the biopsy is negative for rejection the participants may continue with immunosuppression withdrawal. If the biopsy is positive for rejection or if the participant is unable to undergo a biopsy they will be considered to have failed immunosuppression withdrawal.

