6.8 MANAGEMENT OF ACUTE REJECTION

Immunosuppression will be reinstated for all participants who experience biopsy-confirmed rejection or presumed rejection. Investigators may treat rejection according to institutional standard. The following however are recommended guidelines based on previous experience in liver allograft immunosuppression withdrawal trials:

- Allograft dysfunction with *no acute rejection or indeterminate for acute rejection*, and without other explanatory diagnosis should be treated at the discretion of the site investigator with reinstitution of the baseline IS (regimen employed before initiation of IS withdrawal). If liver tests do not improve within 4 weeks, repeat biopsy should be considered prior to further escalation of treatment.
- *Mild acute rejection* should be treated initially with reinstitution of baseline IS. If liver tests do not improve within 2 weeks, dose increase or addition of 20 mg oral prednisolone (or equivalent) should be considered. Corticosteroids will be rapidly tapered down over a 4 week period. A second biopsy can be performed at any time at the investigator's discretion.

- *Moderate acute rejection without jaundice and with mild biochemical abnormalities* should be treated with reinstitution of baseline IS and 20 mg oral prednisolone (or equivalent) with rapid taper down of steroid doses over a 4 week period. If liver tests do not improve within 2 weeks, conversion or addition of another agent should be considered prior to corticosteroids. A second biopsy can be performed at any time at the investigator's discretion.
- *Moderate acute rejection with marked biochemical abnormalities and/or jaundice, severe acute rejection, or chronic rejection*, should be treated according to site standard of care. Antibody treatment should be reserved for steroid-resistant acute rejection proven by repeat liver biopsy.

Participants who experience biopsy-confirmed rejection or presumed rejection prior to completing immunosuppression withdrawal will undergo safety follow-up per Appendix 3. If the episode of biopsy-confirmed rejection or presumed rejection occurs after the completion of immunosuppression withdrawal, the participant will continue on post withdrawal follow-up per Appendix 2. If the participant is restarted on immunosuppression therapy, the subject will be followed concurrently on Appendix 4 (except during the duration of the COVID-19 pandemic).

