9.2.1 Primary Endpoint

The primary endpoint is defined in section 3.3.1.

The primary endpoint will be analyzed using the ITT sample and descriptively summarized with a point estimate and two-sided, 95% confidence interval. All participants who failed to complete immunosuppression withdrawal, regardless of reason, will be considered to have failed the primary endpoint. Participants without a biopsy 52 weeks following completion of immunosuppression withdrawal or who resume immunosuppression prior to 52 weeks will be considered to have failed the primary endpoint. This endpoint will also be analyzed using the PP sample.

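### The primary endpoint does not require the participant to be off immunosuppression on the date of the deciding biopsy, so a restart between week 52 and that biopsy can go unscored

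*SAP*

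**What the plan says.** **Off-drug condition.** SAP 7.2.1 calls a participant tolerant if they have "successfully withdrawn from all immunosuppression and remain off all immunosuppression for 52 weeks", show no sign of rejection from enrollment on, and have a centrally read 52-week biopsy free of rejection and of the Table 1 findings. The footnote in SAP 7.2.2 describes the tolerant as "Subjects who remain off immunosuppression for at least 52 weeks without evidence of rejection and demonstrate histological stability". Protocol 9.2.1 states that participants "who resume immunosuppression prior to 52 weeks will be considered to have failed the primary endpoint".

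**Biopsy date.** Protocol 6.1.1 puts the 52-week biopsy (Visit 204) within 4 weeks either side of its scheduled time. SAP 7.2.1 also admits a for-cause biopsy from the 8 weeks before that visit, and then says: "Any primary endpoint biopsy performed later than 52 weeks (+4 weeks) will be utilized". Both documents count a participant with no 52-week biopsy as not tolerant (SAP 7.2.1, protocol 9.2.1).

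**Restarts.** Protocol 6.8 says that allograft dysfunction with no or indeterminate acute rejection, and no other explanation, "should be treated at the discretion of the site investigator with reinstitution of the baseline IS". Protocol 6.1.1 keeps participants who restart after completing withdrawal on the Appendix 2 visits, which include Visit 204. SAP 7.2.1 notes that dosing is recorded daily and carries no window.

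**The concern.** The off-drug test and the biopsy run on separate clocks. The first stops at week 52. The second can run to week 56 under the protocol window, and further under the SAP's late-biopsy sentence. In the interval between them, no rule looks at drug status.

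The biopsy is there to show that the graft is stable without treatment. Table 1 lists findings that argue against minimal or no immunosuppression, and its absence criteria are informative only if the tissue was taken off drug. Protocol 3.4 itself cites a study in which histological abnormalities improved once low-dose treatment was reintroduced, though it urges caution about those data. Histology obtained on resumed drug could therefore look better than it would have looked without it.

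Where the gap operates it can only add participants to the tolerant group. That status also defines the groups for the primary objective (the senescence and exhaustion comparison), for fibrosis, eGFR and quality of life, and for the age and time-since-transplant model.

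**Working it through.** **1. When the gap opens.** Count weeks from the end of withdrawal. Let R be the week of restart and B the week of the endpoint biopsy.

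| Situation | Rule that applies | Scored |
|---|---|---|
| R before 52 | Protocol 9.2.1; SAP 7.2.1 off-drug test | Non-tolerant |
| Restart for biopsy-proven rejection, any time | Rejection condition | Non-tolerant |
| B before R, with R after 52 | Biopsy taken off drug | Tolerant if clean, as intended |
| 52 < R < B, no evidence of rejection | None | Tolerant if the biopsy is clean |

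Only the last row is a defect. The footnote in SAP 7.2.2 does not close it, because a minimum of 52 weeks does not extend to the biopsy. The protocol's definition of failed withdrawal does not close it either: it lists rejection, presumed rejection without a biopsy, more than 45 weeks to complete withdrawal, and Table 1 findings, but not a later restart without rejection.

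**2. How wide it is.**
- Protocol: B is at most 52 + 4 = 56, so the restart must fall in weeks 52 to 56.
- SAP, natural reading of the late-biopsy sentence: B has no upper limit.
- SAP, alternative reading (biopsies after week 52 but inside the 4-week allowance): the same 4 weeks as the protocol.

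**3. Effect on the primary proportion.** Inputs from protocol 9.3: N = 60, expected proportion 40%, so x = 24. The exact interval is

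lower = Beta⁻¹(0.025; x, n − x + 1), upper = Beta⁻¹(0.975; x + 1, n − x).

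- x = 24: 40.0% (27.6 to 53.5). This reproduces the protocol's figure.
- x = 23: 38.3% (26.1 to 51.8).
- x = 22: 36.7% (24.6 to 50.1).

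One participant is 1/60 = 1.7 points. The documents give no count of affected participants, so one and two are illustrations.

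**4. Effect on the biomarker comparison.** Inputs from protocol 9.3: difference 0.1155, SD 0.152, two-sided 5%. The noncentrality is 0.1155 / (0.152 × √(1/n₁ + 1/n₂)), with n₁ + n₂ − 2 degrees of freedom.

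- 24 against 36: power 0.809 (protocol 0.808).
- 23 against 37: power 0.803.

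Moving one participant to the non-tolerant group, with the effect size held fixed, thus costs almost nothing. Leaving one in the wrong group is 1/24 = 4.2% of the tolerant arm. If that participant had the non-tolerant mean (an assumption), the expected difference would shrink to 0.1155 × 23/24 = 0.1107.

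**The case against.** The strongest reply is that existing rules catch most restarts, and much of it stands.

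- **Rejection is already excluded.** Biopsy-proven rejection at any time disqualifies. A reader might infer that a participant treated for presumed rejection just after week 52, with a negative biopsy, would be scored tolerant. The documents do not clearly support that. Protocol 6.7.3 says "Participants with presumed rejection must undergo a biopsy within a week after initiation of treatment for allograft dysfunction" unless contraindicated, and lets withdrawal continue if that biopsy is negative. But protocol 6.10.2.2 combines the central read with the treatment given when rejection outcomes are determined, so such a case is arguably evidence of rejection. Nor does the substitution rule make that biopsy the endpoint biopsy, since it covers only the 8 weeks before Visit 204.
- **Dysfunction normally brings an earlier biopsy.** Under protocol 6.6.1, unexplained dysfunction beyond 72 hours requires a for-cause biopsy. A participant restarted under protocol 6.8 without rejection would normally have histology from before the restart. That narrows the case but does not remove it: the SAP does not say that this biopsy, rather than a later scheduled one, decides the endpoint. A restart for a non-graft reason need not involve a for-cause biopsy at all.
- **Unlimited exposure is not certain.** A reader might infer that both documents accept a biopsy at any date. The SAP sentence most naturally says so, but it can be read as confined to the 4-week allowance, and the missing-biopsy rule pulls that way. The protocol has no late-biopsy allowance.
- **The 3-year endpoint is not inflated.** One might infer that the error carries through as a success at year 3. SAP Table 7-2 requires participants to remain off all immunosuppression to that point, so someone still on drug counts there as a failure.
- **The effect is small.** One participant moves a descriptive estimate by 1.7 points, within an interval about 26 points wide (53.5 − 27.6 = 25.9).

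**Conclusion.** The gap is real but narrow. Followed literally, the SAP can score as tolerant a participant who restarted after week 52 without evidence of rejection and whose endpoint biopsy came after the restart. Protocol 9.2.1 shares the gap only in weeks 52 to 56. In the SAP it is open-ended on the more natural reading of the late-biopsy sentence, which is not the only reading.

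The direction is fixed: any error raises the tolerance proportion. The frequency is unknown and may be zero. The 1.7 points per participant rests on N = 60; the intervals also rest on the planned 24 tolerant participants. The published precision and power figures are correct and are not in dispute. The point deserves a change because the trial is open label, tolerance status defines most of the group comparisons, and the rule is better set in advance than when a case arises.

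**What to change.** In SAP 7.2.1, the footnote in SAP 7.2.2 and protocol 9.2.1:

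1. Define tolerance as off all immunosuppression from completion of withdrawal through the later of week 52 and the date of the primary-endpoint biopsy.
2. State that a biopsy taken after a restart is not an eligible primary-endpoint biopsy. If an eligible biopsy was taken before the restart, the existing 52-week requirement applies unchanged.
3. Reconcile the late-biopsy sentence with the Visit 204 window and the missing-biopsy rule: say whether a biopsy after week 56 counts and, if so, up to what date.
4. Say which biopsy decides the endpoint when a for-cause biopsy after week 52 precedes the scheduled one, and whether presumed rejection with a negative biopsy counts as evidence of rejection.

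The cost is a few sentences in the SAP and one in the protocol. No new data are needed, because daily dosing records already allow the check. This changes scoring only, not patient management. The downside is a possibly slightly lower tolerance proportion.
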